1.0 Objectives / Specific Aims

The objective of this study is to determine whether the application of povidone-iodine ophthalmic solution onto the ocular surface causes a change in respiration in children undergoing strabismus surgery with general anesthesia.

Hypothesis: The application of povidone-iodine ophthalmic solution to the ocular surface causes a change in respiration in children during general anesthesia prior to strabismus surgery.

2.0 Background

Primitive neural reflexes are often unmasked during anesthesia. This is most likely due to an imbalance in the effect of anesthetics on inhibitory and excitatory neurons. The oculo cardiac reflex (OCR) is a well-known reflex that occurs when traction is applied to an extra-ocular muscle. The afferent limb of the reflex is mediated by sensory branches of the trigeminal nerve and the efferent limb is mediated by the vagus nerve. Stimulation of a branch of the trigeminal nerve causes an increase in vagal activity that can cause a variety of changes in heart rate and rhythm. Although the OCR has been reported to cause atrioventricular block, premature ventricular contractions (PVCs), ventricular tachycardia, and sinus arrest, bradycardia is the most consistently reported finding during anesthesia.

The OCR has been known to occur with strabismus surgery for many decades and is correlated with traction on the extraocular muscles.^{1,2} If the decrease in heart rate is significant enough to cause a decrease in cardiac output and/or blood pressure, the intravenous administration of glycopyrrolate or atropine effectively increases the heart rate in most patients. Less well-known triggers of the trigemino-vagal reflex during anesthesia involve noxious stimuli to the mandible or skull base.³⁻⁵ Changes in respiratory pattern (e.g. apnea, dachypnea, and bradypnea) have not been described with the OCR that occurs during anesthesia.

The diving reflex that occurs in diving birds and mammals is characterized by cessation of respiration, decrease in heart rate, and diversion of blood flow to critical organs (brain, heart, kidneys) from less critical tissue beds.⁶ The diving reflex is initiated in these animals when the head and face are submerged resulting in stimulation of the trigeminal nerve. A diving-type reflex has been described in humans, most notably in near-drowning victims. Activation of this reflex may explain the survival of humans, especially children,

submerged in cold water for 30 to 40 minutes. The diving reflex has also been implicated in the pathophysiology of sudden infant death syndrome (SIDS).⁷ Despite the similarity of the OCR and the diving reflex, the relationship between the two is unknown.^{8,9}

In 2015, an observational study was published that described apnea after the application of povidone-iodine ophthalmic solution on respiration. All of those children were breathing sevoflurane spontaneously via a laryngeal mask airway (LMA). Why this was not observed previously is not clear. Prior to the introduction of the LMA into clinical practice, most children undergoing strabismus surgery underwent tracheal intubation and were managed with controlled or assisted ventilation. A brief period of apnea or changes in respiration were, consequently, not obvious. For the vast majority of children undergoing strabismus surgery throughout the United States (including at MUSC), standard airway management during anesthesia practice is with an LMA. The predominant inhaled anesthetic administered is sevoflurane.

Povidone-iodine solution has become the standard for disinfection of the eye prior to surgery.^{11, 12} Povidone- iodine solution has been typically formulated as a 10% solution. For surgical eye preparations, the 10% solution is diluted to produce a 5% solution. Recently, a specially formulated 5% Betadine® ophthalmic solution (manufactured for Alcon Laboratories, Fort Worth, Texas by Catalent Pharma Solutions, LLC, Woodstock, IL) was introduced and has become a standard for surgical eye preparation. Ophthalmic balanced salt solution (BSS) is an isotonic solution specifically formulated for irrigation of eye tissues. BSS is used in nearly all eye surgeries for irrigation. These solutions are both FDA approved.

The objective of this study is to try to begin delineating the physiology of a potential reflex change in respiratory pattern initiated by a mechanical or chemical stimulus. This study is the first step in the study of this reflex. The results of this study will be used to develop further studies aimed at complete definition of this reflex.

3.0 Intervention to be studied

The effect of the application of povidone-iodine ophthalmic solution on the ocular surface on respiration will be compared to the effect on respiration of the application of the application of ophthalmic BSS on the ocular surface during general anesthesia. Both of these solutions are FDA approved for use in this manner and this intervention will begin once a steady state of anesthesia is achieved by means of the standard of care. After the

induction of general anesthesia and at the time the patient is ready for surgical preparation of the eyes, subjects will first have their average peak to peak interval for respiration measured at a steady state of anesthesia, using capnography. This will give us a baseline for measuring a change in respiratory rate. They will then have one of two solutions applied to the ocular surface of each eye. It is this application of eye solution that is the main study intervention. The solution to be used is determined by randomization upon enrollment and will either be 3 drops of povidone-iodine ophthalmic solution in each eye (Group A) or 3 drops of BSS in each eye (Group B). The eye solution intervention period will take less than 5 minutes and will cause either only a slight delay or no delay in the surgical time. The only other intervention is the collection of data after induction (but just prior to IV insertion), as well as before and after the drops of eye solution are delivered.

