10.0 Study Design / Methods

Once it is confirmed that the attending anesthesiologist has both examined the patient and decided on an anesthesia plan that aligns with our inclusion criteria, the patient and their family will be consented. If the patient is included in the study, the study member will randomize the patient to one of two groups: Group A - povidone-iodine ophthalmic solution, or Group B - ophthalmic balanced salt solution. This randomization will be determined using a simple randomization scheme provided by the study's statistician. All decisions regarding anesthesia care, including the indication for preoperative pharmacologic anxiolysis, will be made by the attending pediatric anesthesiologist. The case will then progress as it would without study involvement and the patient would be brought into the operating room and anesthesia would be administered. The standard of care course of anesthesia includes:

- Inhalation induction with oxygen in sevoflurane
- Insertion of a peripheral intravenous catheter after induction of anesthesia
- After a suitable depth of anesthesia is achieved, a laryngeal mask airway of an appropriate size will be inserted and secured

The only deviation from standard of care during the above process is the collection of data after induction, just prior to IV insertion. These data points are heart rate (HR), blood pressure (BP), respiratory rate (RR), arterial oxygen saturation (SaO₂), end tidal CO₂ (ETCO₂), inspiratory sevoflurane (InspSevo), and expiratory sevoflurane (ExpSevo). This data will be collected by a study member in real, intraoperative time. The collection of data will not affect the progression of standard anesthesia practice, as the data collector will not be involved in the clinical care of the patient. Once the airway is secured and the patient has reached a steady state of anesthesia, the main study intervention will then commence. We first would like to obtain the patient's average peak to peak interval for respiration at this steady state of anesthesia, as measured from the capnography. To do this, the research member in the room for data collection will use the iPhone stopwatch application and its 'lap button' feature to collect the respiration peak intervals (in seconds)

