12.0 Data Management

Descriptive statistics by treatment group will be evaluated for all demographic and procedural characteristics. The goal of the study is to determine if there is a significant difference in the change in respiratory response immediately following administration of saline or povidone-iodine solution in patients undergoing strabismus surgery. The primary outcome is the difference between the peak to peak interval time from the capnograph measured before saline or povidone-iodine administration versus after administration. Pre-exposure peak to peak interval will be measured as the average time between peaks for five breaths prior to administration. Post-exposure peak to peak interval will only be evaluated as the time between the two peaks at saline or povidone-iodine administration. Differences in the change in peak to peak interval time between the saline and povidone-iodine exposure groups will be evaluated using a linear regression approach. The model will include a treatment effect and will additionally control for patient age, history of prematurity, and use of any pre-medication to account for other factors thought to be associated with respiratory rate. We anticipate no change in peak to peak interval time in the saline group with variability of ± 4 seconds. A sample size of 50 patients per treatment group (100 patients total) provides $>80\%$ power to detect an increase in change in peak to peak interval of 2.5 seconds in the povidone-iodine group compared to the saline group assuming equal variance between the two groups using a 2-sided test with significance level set at alpha = 0.05. If the variability of the povidone-iodine group is larger, for example a variability of 8 seconds, compared to 4 seconds in the saline groups we still have 80% power to detect an increase in the povidone-iodine group of approximately 4 seconds.

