14.0 Withdrawal of Subjects (if applicable)

Subjects will be withdrawn from the study if any changes need to be made to the anesthesia plan that do not align with the inclusion/ exclusion criteria of the study; e.g. if any airway intervention other than an LMA is required at the start of surgery.

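### The arm is assigned at enrolment, before LMA placement, steady state and the baseline breaths, with no concealment described, so withdrawals and the baseline moment could differ by arm

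*Protocol*

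**What the plan says.** Protocol 3.0 fixes the time of allocation: "The solution to be used is determined by randomization upon enrollment". Section 10.0 agrees. The attending anesthesiologist has examined the child and "decided on an anesthesia plan that aligns with our inclusion criteria, the patient and their family will be consented"; then "the study member will randomize the patient to one of two groups". The method is simple randomisation from a scheme supplied by the statistician. Neither document says how the scheme is concealed or who learns the result.

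The rest of 10.0 describes what follows. On discretion it says: "All decisions regarding anesthesia care, including the indication for preoperative pharmacologic anxiolysis, will be made by the attending pediatric anesthesiologist". Induction, IV insertion and LMA placement come next, and then: "Once the airway is secured and the patient has reached a steady state of anesthesia, the main study intervention will then commence". The five baseline breaths are timed at that point, and the drops come after them. No criterion for steady state is given.

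Section 14.0 provides that "Subjects will be withdrawn from the study if any changes need to be made to the anesthesia plan" and those changes breach the eligibility criteria. Its example is a need for a different airway when surgery starts. Neither document defines an analysis set or says how withdrawn children are counted.

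On the analysis, protocol 12.0 takes the change from the five-breath baseline as the primary outcome, and its model "will additionally control for patient age, history of prematurity, and use of any pre-medication". The SAP model lists age, pre-term birth, history of apnea and pre-drop breath duration. It does not list premedication.

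**The concern.** The question is the acute effect of the drops in a child already breathing steadily through an LMA. The comparison should therefore start at that moment, and nothing earlier needs the arm to be known. Assigning it in the holding area opens an interval in which three things happen under a fixed allocation.

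- **Withdrawals.** A child whose airway plan changes in this interval leaves after being randomised. If the decision to withdraw is coloured by the arm, the remaining groups are no longer the randomised ones.
- **The baseline moment.** Someone judges when anaesthesia is steady and when to time the breaths. That baseline is half of the protocol's change outcome and a covariate in the SAP model, and the ten pre-drop breaths enter the SAP's secondary definition of a change in respiration.
- **Lead-in care.** Anaesthetic care, and possibly premedication, is at the attending's discretion during this time.

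Bias is at stake here, not precision. These events come before the drops, so the solution cannot cause them. A systematic difference between arms requires that someone who influences them knows the arm. The documents leave that possible.

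**Working it through.** **Order of events**, from protocol 3.0, 10.0, 13.0's neighbour 14.0 and section 12.0:

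1. Anaesthesia plan decided, then consent.
2. Arm assigned by a study member.
3. Induction, IV, LMA, steady state judged.
4. Five baseline breaths.
5. Drops, then post-drop data.
6. Surgery proceeds.

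Steps 3 and 4 lie between allocation and the first use of the arm. The premedication decision belongs to step 1 or to the time after step 2; the text does not settle which. Withdrawal under 14.0 can occur at step 3, and on its own example perhaps as late as step 6.

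**The plan's own figure.** Inputs from protocol 12.0: 50 per arm, difference 2.5 s, variability 4 s (read as a standard deviation), two-sided alpha 0.05.

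- Standard error = 4 × √(2/50) = 0.80 s.
- 2.5/0.80 = 3.125, and 3.125 − 1.96 = 1.165, which gives power 87.8% (87.2% by the noncentral t). The stated figure of more than 80% is reproduced.
- If all ten of the children above 100 were lost from one arm (55 against 45), power is 86.8%. The sample size is not the problem.

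**Selective withdrawal.** Protocol 6.0 enrols about 110 (55 per arm) and 12.0 needs 100, so 110 − 100 = 10 are spare, or 10/110 = 9.1%. The protocol does not say that these ten are a withdrawal allowance; I use the number only to set a scale. Assume all ten losses fall in one arm, and that the lost children's mean differs by d = 2.5 to 5 s. The documents give no figure for d.

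Write F for the full-arm mean, R for the mean of the 45 retained and L for the mean of the 10 lost, so 55F = 45R + 10L.

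| d measured from | Shift, F − R | d = 2.5 s | d = 5 s | Share of 2.5 s target |
|---|---|---|---|---|
| Retained children (L = R + d) | 10d/55 | 0.45 s | 0.91 s | 18 to 36% |
| Full-arm mean (L = F + d) | 10d/45 | 0.56 s | 1.11 s | 22 to 44% |

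This case is extreme. If each loss were equally likely in either arm, all ten would fall in the same arm with probability 2 × (1/2)^10 = 0.2%. With losses balanced and unrelated to response, the bias is zero.

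**Arm-influenced baseline.** Suppose the two arms differ systematically by b seconds in the change outcome because of the moment chosen for baseline, with no true effect of the drops (assumed; 50 per arm, standard deviation 4 s). The two-sided rejection rate rises from 5% as follows.

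| b | Rejection rate |
|---|---|
| 0.25 s | 6.1% |
| 0.5 s | 9.5% |
| 1.0 s | 23.6% |

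These rates show how sensitive the test is to such a shift. They are not evidence that one occurs.

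**The case against.** The strongest reply is that early allocation with proper concealment is unbiased. If the anaesthesia team does not know the arm, withdrawals and lead-in care differ only by chance. No text says that the attending is told the allocation: a study member randomises, and the data collector takes no part in clinical care. This stands as far as it goes. It makes the concern conditional, but it does not remove it, because neither document describes concealment or masking and the data collector's separation from care does not keep anyone unaware of the arm.

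A second reply is that the outcome protects itself. The protocol analyses within-child change and the SAP adjusts for pre-drop breath duration, so part of any effect on resting rate is removed. This also stands. What remains is loss of children related to their response, and a baseline taken at a moment influenced by the arm.

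Three stronger readings are tempting, and the documents do not support them.

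- **A reader might infer that premedication is decided after allocation and so is not a baseline covariate.** The sentence on anxiolysis says who decides, not when, and the plan is settled before consent. Its place after randomisation is only the order of the text. Premedication is also a covariate in the protocol model alone.
- **A reader might infer that care is given with the arm known.** That is possible but not shown.
- **A reader might infer that later allocation turns every withdrawal into a screen failure.** The example in 14.0 is tied to the start of surgery, which by 10.0 follows the drops, so some withdrawals could still come after allocation.

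**Conclusion.** The point holds in conditional form. Randomisation precedes induction, LMA placement, an undefined steady-state judgement and the baseline breaths, and no concealment is described. If staff know the arm, withdrawals, lead-in care and the choice of baseline moment could differ between arms; if they do not, any difference is chance.

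The documents give no figure from which to estimate the size of any bias. Under the extreme assumption of ten losses from one arm with d of 2.5 to 5 s, the arm mean moves by 0.45 to 0.91 s, or 0.56 to 1.11 s if d is measured from the full-arm mean. The stated power is sound and unaffected. The change is worth making because it closes a route to bias at very little cost, not because bias has been shown.

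**What to change.** In protocol 3.0 and 10.0, keep consent in the holding area, but open the next concealed allocation only after the LMA is secured, steady state is declared and the baseline breaths are recorded, immediately before the drops. In 14.0 and the SAP, state that children whose airway plan changes before that point are pre-randomisation screen failures, and that any withdrawn later stay in the randomised set and are reported by arm with reasons. Baseline breathing and premedication then both precede allocation, whichever model is used.

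The cost is protocol wording, bringing the allocation into the operating room, having both solutions on hand, and seconds added before the drops. No extra staff or visits are needed. The change does not address who times the breaths after the drops, which is a separate matter.

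The SAP is written in the past tense. If enrolment is already complete, the sponsor should report post-randomisation withdrawals, premedication and baseline intervals by arm, and state who knew the allocation and when.

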4.0 Study Endpoints (if applicable)

The effect on respiration will be recorded upon application of either the 3 drops of povidone-iodine ophthalmic solution or 3 drops of BSS in each eye. The presence of any respiratory effect – specifically a change in respiratory rate – will be the primary endpoint for this study. Changes in respiratory pattern will be detected and measured by observation of the capnograph, which measures breath by breath CO₂.^{13, 14} The capnograph is a standard monitor employed during the standard administration of general anesthesia.¹⁵

5.0 Inclusion and Exclusion Criteria/ Study Population

Operating room schedules will be screened the day prior to surgery and eligible candidates (their families) will be invited to participate in the study on the morning of surgery in the preoperative holding area. The primary reason for including children is that strabismus is normally corrected during childhood and strabismus surgery is of importance because, as was mentioned previously, the oculo cardiac reflex has been known to occur with strabismus surgery.

Inclusion Criteria

- *Children 17 years and less*
- *Scheduled for strabismus surgery*
- *Anesthesia plan includes inhalational induction with sevoflurane and the use of a laryngeal mask airway (LMA) with spontaneous ventilation, per the attending anesthesiologist.*

Exclusion Criteria

- *History of an adverse reaction to iodine*
- *History of any thyroid disease*
- *Patients who require tracheal intubation, as determined by the attending anesthesiologist; e.g. craniofacial anomalies.*
- *Patients with a contraindication to sevoflurane, such as malignant hyperthermia or severe left ventricular dysfunction.*
- *Inability or unwillingness of the subject or legal guardian/ representative to give informed consent.*

6.0 Number of Subjects

We will enroll approximately 110 patients in this study to include 55 patients for each randomized ‘treatment’ group. Please refer to section 12.0 for the justification behind this enrollment number.

7.0 Setting

This study will be conducted solely in the perioperative areas of MUSC.

8.0 Recruitment Methods

The surgical schedule will be reviewed by a member of the study team on the day prior to surgery to identify patients undergoing strabismus surgery. A chart review will be performed to ensure that they fall under proper inclusion criteria. Furthermore, the study team will contact the attending anesthesiologist who will be working the potential study candidate’s case to make sure the anesthesia plan does not exclude the patient from the study. Patients will be approached on the morning of surgery in the preoperative holding area of MUSC by a study team member and the consent process will proceed.

9.0 Consent Process

Upon approaching the patient in the perioperative holding area of MUSC, the study will be thoroughly explained to the patient (if old enough to comprehend), as well as the family of the patient. The consent and HIPAA forms will be presented and explained and the family will be given the opportunity and time to read through the forms. Any questions they might have about the study or either of the forms will be answered by the study member and/or the attending anesthesiologist. The parents or guardian(s) will then be asked to sign the consent form, as the patients will be under the age of 18. If they patient

is over the age of 12, they will also be asked to give assent for study participation and the proper form for this will be presented to them and explained prior to obtaining their signature.

10.0 Study Design / Methods

Once it is confirmed that the attending anesthesiologist has both examined the patient and decided on an anesthesia plan that aligns with our inclusion criteria, the patient and their family will be consented. If the patient is included in the study, the study member will randomize the patient to one of two groups: Group A - povidone-iodine ophthalmic solution, or Group B - ophthalmic balanced salt solution. This randomization will be determined using a simple randomization scheme provided by the study's statistician. All decisions regarding anesthesia care, including the indication for preoperative pharmacologic anxiolysis, will be made by the attending pediatric anesthesiologist. The case will then progress as it would without study involvement and the patient would be brought into the operating room and anesthesia would be administered. The standard of care course of anesthesia includes:

- Inhalation induction with oxygen in sevoflurane
- Insertion of a peripheral intravenous catheter after induction of anesthesia
- After a suitable depth of anesthesia is achieved, a laryngeal mask airway of an appropriate size will be inserted and secured

The only deviation from standard of care during the above process is the collection of data after induction, just prior to IV insertion. These data points are heart rate (HR), blood pressure (BP), respiratory rate (RR), arterial oxygen saturation (SaO₂), end tidal CO₂ (ETCO₂), inspiratory sevoflurane (InspSevo), and expiratory sevoflurane (ExpSevo). This data will be collected by a study member in real, intraoperative time. The collection of data will not affect the progression of standard anesthesia practice, as the data collector will not be involved in the clinical care of the patient. Once the airway is secured and the patient has reached a steady state of anesthesia, the main study intervention will then commence. We first would like to obtain the patient's average peak to peak interval for respiration at this steady state of anesthesia, as measured from the capnography. To do this, the research member in the room for data collection will use the iPhone stopwatch application and its 'lap button' feature to collect the respiration peak intervals (in seconds)

for 5 breaths. Specifically, at the patient's peak inspiration (as seen on the capnography), the study member will start the stopwatch and proceed to hit the 'lap' button for the next 5 consecutive inspiration peaks. These data intervals will be recorded on the data sheet after the 5 breaths are over, as the intervals are conveniently stored and numbered below the stopwatch in the app. We will do this to establish an average baseline respiratory rate for each individual patient. Next, patients who are randomized to Group A will receive three drops of povidone-iodine ophthalmic solution in each eye, with the right eye to receive the drops first. Group B will receive three drops in each eye of ophthalmic balanced salt solution. Similarly, the right eye will receive the drops first; the reason being that we know that there are differences in sympathetic stimulation on the right side of the face vs left (e.g. termination of supraventricular tachycardia) and although we don't know if this effects OCR, we chose to standardize right eye first. The eye drops will be administered by the study anesthesiologist. After application of either solution to the eyes of the patient, any change in ventilation can be detected and timed by observation of the capnography (end-tidal carbon dioxide) and direct observation of the chest wall with use of the iPhone stopwatch feature again. The capnograph is a standard monitor of respiration used during the administration of general anesthesia. Data collected at this time will include whether or not there was a change in respiration, what this change in respiration was, if assisted ventilation was required, how long assisted ventilation was required (if applicable), HR, BP, RR, SaO_2 , ETCO_2 , InspSevo, and ExpSevo. This study intervention and data collection will take less than 5 minutes and the surgical team will then progress with the case as they normally would.

Other data to be collected is as follows:

- Attending anesthesiologist and CRNA
- Age
- Weight
- Sex
- Co-existing diseases
- If the patient was a pre-term birth and if yes, the estimated gestational age at birth
- If premedication was given and if yes, what medication and dose
- If N_2O was used during inhalational induction

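### No masking of the person who hand-times the breaths and no concealment of the allocation is described, so the primary outcome is open to observer bias

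*Protocol*

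**What the plan says.** All the operational detail is in Protocol Section 10.0.

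- **Allocation.** After consent and before the operating room, "the study member will randomize the patient to one of two groups". Section 3.0 also places randomization at enrollment.
- **Data collection.** "This data will be collected by a study member in real, intraoperative time", and "the data collector will not be involved in the clinical care of the patient".
- **Baseline timing.** "the research member in the room for data collection will use the iPhone stopwatch application". In detail, "the study member will start the stopwatch and proceed to hit the 'lap' button for the next 5 consecutive inspiration peaks".
- **Drops.** "The eye drops will be administered by the study anesthesiologist".
- **Post-drop timing.** Changes are found and timed from the capnograph and by "direct observation of the chest wall with use of the iPhone stopwatch feature again". The data sheet also records "whether or not there was a change in respiration, what this change in respiration was", with no criterion given.

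Protocol Section 12.0 makes the primary outcome the change from the mean of five baseline intervals to a single interval at administration. The SAP instead models breath duration over 15 post-drop breaths, and it derives a yes/no change in respiration by a rule applied to each child's own durations.

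Neither document mentions blinding, masking or allocation concealment for anyone.

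**The concern.** The primary measurement depends on a person pressing a button at a peak seen on a screen. The arm has been assigned before the first baseline breath is timed, and the plan does nothing to keep it from that person. Even a timer who is not told the arm is in the room watching the child's chest while the solution goes into the eyes.

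There is room for discretion. Under Section 12.0 the post-drop value is one interval, yet administration consists of three drops in each eye, right eye first. More than one breath could count as the one at administration, and the text does not say which. If peak marking or interval choice differs by arm, the difference goes straight into the treatment estimate. Adjustment for age, prematurity and premedication cannot remove an error that follows the arm.

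**Working it through.** **Inputs from Protocol Section 12.0.** 50 analysed per arm; variability of change 4 s, read here as an SD; target difference 2.5 s; two-sided alpha 0.05. The section's alternative is 8 s in the povidone-iodine arm against 4 s in the saline arm. The size of any differential timing error, b, is not in the documents and is assumed below.

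**Step 1: reproduce the stated power.** SE = 4 × √(2/50) = 0.8 s. By the normal approximation, 2.5/0.8 = 3.125, and 3.125 − 1.96 = 1.165, which gives 87.8%. The noncentral t with 98 df gives 87.2%. Both agree with the stated figure of more than 80%.

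**Step 2: observed difference needed for p = 0.05.** t(0.975, 98 df) × 0.8 = 1.59 s.

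**Step 3: false-positive rate with no true effect and a differential error b.** The test statistic follows a noncentral t with 98 df and noncentrality b/0.8. In the 8 s versus 4 s case, SE = √((64 + 16)/50) = 1.265 s and a Welch test is used.

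| Assumed b (s) | b/0.8 | Rate, SD 4 s in both arms | Rate, SD 8 s vs 4 s |
|---|---|---|---|
| 0.1 | 0.125 | 5.2% | 5.1% |
| 0.25 | 0.3125 | 6.1% | 5.4% |
| 0.5 | 0.625 | 9.5% | 6.8% |
| 1.0 | 1.25 | 23.6% | 12.2% |

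Whatever the SD, the estimate itself moves by b: 0.5 s is 0.5/2.5 = 20% of the target difference, and 1.0 s is 40%.

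**Step 4: where a timing error would enter.** Consecutive laps share endpoints, so the mean of five baseline intervals equals (last press − first press)/5. A last press that is 0.5 s late adds 0.5/5 = 0.1 s to the baseline mean. The post-drop value is one interval, so the same late closing press adds the full 0.5 s. The exposure lies mainly in the post-drop reading.

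Steps 2 and 3 use a two-sample test in place of the adjusted regression of Section 12.0. They do not carry over to the SAP's mixed model with 15 Bonferroni-corrected comparisons.

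**The case against.** Several stronger readings are tempting, and the documents do not support them.

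- **That the timer knows the arm.** A reader might infer this because the term study member is used both for randomizing and for timing. The inference is reasonable, but no section says that one person does both or that the timer is told. What can be said is that no masking is described.
- **That the analysed yes/no outcome is a staff call.** The bedside item is a data-sheet field for which Section 12.0 plans no analysis. The SAP's outcome is calculated: a duration more than twice the interquartile range above the child's own 75th percentile. Bias could reach it only through the durations, and the SAP does not say how the 10 pre-drop and 15 post-drop durations were obtained.
- **That the choice of one interval decides the result.** This fits Section 12.0 but not the SAP, which models 15 post-drop breaths.
- **That the bias is present and favours an effect.** The hypothesis is of a change and the test is two-sided. Lack of masking creates a risk; it shows neither presence nor direction.

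The size can also be challenged. Peaks are visible on the capnograph, a constant press delay cancels within an interval, and a late press that lengthens one interval shortens the next. An average difference between arms of 0.5 s or more is therefore demanding. That argument stands for press error within a run of breaths. It is weaker for Section 12.0's single post-drop interval, where nothing averages out and the choice of breath is open.

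**Conclusion.** The point holds in limited form. The plan hand-times its primary outcome with no described masking of the timer and no described concealment, after allocation has been made. This leaves the primary interval, and any SAP outcome built on hand-timed durations, open to observer bias that the planned analysis cannot correct.

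The size is unknown. Under the stated SD of 4 s and 50 per arm, assumed differential errors of 0.1 and 0.25 s barely matter (about 5% and 6%), while 0.5 and 1.0 s raise the false-positive rate to about 10% and 24%. The inflation is smaller in the protocol's own unequal-variance case. These figures show vulnerability under assumptions, not that bias occurred. Stated power and sample size are unaffected.

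A reader might also infer that masking needs no additional staff, since the person giving the drops and the data collector are already separate roles. That is plausible, but the documents do not establish it.

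**What to change.** In Protocol Section 10.0:

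1. Have someone other than the timer hold the allocation, for example in a sealed envelope that the study anesthesiologist opens after the baseline breaths are recorded.
2. Do not tell the timer the arm, and announce the moment of each application verbally.
3. Keep the eyes and the solution out of the timer's view until the last post-drop breath is timed, leaving the capnograph and chest visible.
4. Enter the arm on the data sheet only afterwards.

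If the monitor can export a stored capnograph trace, which the documents do not say, a masked reader timing from that trace would be an alternative. Where masking is not feasible, or for data already collected without it, state that assessment was open-label.

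The cost is envelopes, a screen or drape, a verbal cue and a paragraph of procedure. Responsibility for opening the allocation moves from the study member to the anesthesiologist. Masking may sometimes fail because the solutions may look different, so the protocol should ask for any unmasking to be recorded.
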